11.0 Provisions to Monitor the Data to Ensure the Safety of Subjects

The principal investigator will be responsible for the overall monitoring of the data and safety of study participants. The PI's plan for ensuring safety and data integrity follows.

Quality Control. QC will include regular data verification at weekly meetings with the PI, Co-Is and study personnel. This will include verification of the documentation (Integrity of the Consent and HIPPA, scores on the Assessments, MRI scanning information), study progress and participant status, any adverse events, and any protocol deviations. Events determined by the PI to be unanticipated problems involving risks to subjects or others (UPIRTSOs) will be reported by the PI to the IRB as soon as possible and no more than 10 working days per policy.

Safety Training. Before any investigator or assistant is allowed to enter the scanner room, they are required to take an extensive MRI safety course (with annual refresher courses) that cover powering down (or quenching) the magnet for patient safety and with established procedures for expediting participant contact with emergency medical personnel, should the need arise. These courses are run by the MUSC Center for Biomedical Imaging and are a prerequisite for obtaining privileges to book and use scanner time. Prior to administering TMS all personnel must be trained and certified by [name]/[name].

Seizure Risk. Participants will already be lying down on the scanner bed during scans or reclined in a chair during rTMS. In the event of a seizure in the scanner, participants will be taken out of the magnet bore immediately and the barriers on both sides of the detachable bed will be raised to prevent injuries from falls. This event will qualify as a medical emergency and procedures outlined below will be followed.

Medical Emergencies:

1. Emergency responding in the scanner is facilitated by having two research staff running a scan.

In the event of an emergency, one of these individuals remains with the participant and undocks the scanner bed from the magnet bore. This bed can easily be wheeled out of the scan room to facilitate speedy access to arriving emergency medical personnel. The second researcher calls 9-1-1 from the scanner suite and gives details of the participant's level of medical distress and location. Next, this person goes out to the front of the scanner building to flag down arriving emergency personnel and to direct them to the participant.

2. [name] and [name] are licensed physicians and will be on call during all sessions and rTMS sessions (or a similarly trained physician) to respond to any more subtle potential medical situations arising from doing TMS/fMRI. [name] will be responsible for training research personnel in detecting the onset of seizures.

3. These guidelines are in full agreement with the Center for Biomedical Imaging safety protocols and with published guidelines by a panel of experts in conducting TMS/rTMS and TMS/neuroimaging work for both research and clinical purposes⁹⁵.

Ethical Research Practices. Ethical guidelines for clinical research will be followed strictly and all information obtained in the study will be kept strictly confidential. Data will be assigned coded identifiers and all names will be removed from study assessment and outcome data. Files linking participant names or identifying information to the coded identifier will be stored in a password-protected file, on a password protected desktop computer in a locked laboratory. Demographic and other identifying information will be stored separately from consent forms to eliminate the possibility of participant identification; signed consent forms will be locked in secure cabinets separate from data files. The files linking names to IDs will be deleted at the conclusion of the research project. De-identified data will be stored indefinitely following the conclusion of the project. Only the PI and active research staff will have access to the de-identified data. The PI and all research staff and mentors will be responsible for and will comply with mandated reporting rules. All researchers will be obligated to demonstrate that they have remained abreast of all guidelines and rules related to the Health Insurance Portability and Accountability Act (HIPAA). Each member of the research staff will complete focused training on each task for which they are responsible and will perform ongoing quality control for others performing similar work. The PI and/or study coordinator will produce quarterly administrative reports describing study progress including accrual, demographics, and participants' status. Reports will describe adherence to inclusion/exclusion criteria and the study protocol in addition to any unanticipated problems in the category of risks to participants or others as well as any adverse events. All collected data will be obtained for research (and participant safety) purposes only.

Other protections against risk. In designing this trial, the research team constantly struggled with the tension between adding more tests or interventions and participant burden. As was discovered in the pilot study by [name] and colleagues⁸⁶, this design is feasible, does not impose unreasonable expectations of time or effort, or expose patients to risks or limit them from the best available care.

Adverse Events & Trial Safety. Potential conflicts of interest will be reported using the NIH rules for disclosure. Adverse Events (AEs)/Serious Adverse Events (SAEs) occurring during the course of the project will be collected, documented, and reported in accordance with protocol and IRB reporting requirements. All research staff involved with adverse event reporting will receive general and protocol specific AE/SAE training including identification, assessment and evaluation, and documentation and reporting. A research specialist will identify any potential adverse events during the course of the study from participant self-report and administration of the visit assessments and procedures. The research assistant will provide information to the PI, who will be responsible for AE/SAE assessment and evaluation including a determination of seriousness and study relatedness.

An Adverse Event (AE) is defined as any unwanted change, physically, psychologically or behaviorally, that occurs in a study participant during the course of the trial is an adverse event. A Serious Adverse Event (SAE) is defined as an adverse event that has one of the following outcomes:

- Results in death,
- Is life-threatening,

- Requires inpatient hospitalization or prolongation of existing hospitalization,
- Results in persistent or significant disability/incapacity, OR
- Requires intervention to prevent one of the above outcomes.

AEs/SAEs are documented and reported as per protocol and IRB requirements. Research staff will identify adverse events and obtain all available information to assess severity, seriousness, study relatedness, expectedness, outcome and the need for change or discontinuation in the study intervention. Adverse events are generally documented on AE Logs and AE Case Report Forms (CRFs). Additional relevant AE information if available should be documented in a progress note in the research record as appropriate to allow monitoring and evaluating of the AE. If the AE meets the definition for serious, appropriate SAE protocol specific reporting forms are completed and disseminated to the appropriate persons and within the designated timeframes as indicated above. For each AE/SAE recorded, the research staff will follow the AE/SAE until resolution, stabilization or until the participant is no longer in the study as stated in the protocol. When a reportable SAE is identified, the research staff will notify the MUSC Institutional Review Board (IRB) within 24 hours and complete the AE report form in conjunction with the PI. The MUSC IRB meets monthly and is located at [name]. Communication with the IRB is through email, memos, official IRB forms, and online reporting.

If complete information is not available when the initial 24-hour SAE report is disseminated, follow-up information will be gathered to enable a complete assessment and outcome of the event. This information may include hospital discharge records, autopsy reports, clinic records, etc. The research staff will attach copies of source documents to the SAE report for review by the PI.

We will report adverse events to the Medical University of South Carolina (MUSC) Institutional Review Board (IRB), but no later than 10 working days after the investigator first learns of the event. The MUSC IRB AE reporting requirements are as follows: All deaths that occur during the study or 30 days post termination from the study are required to be reported as adverse events even if they are expected or unrelated. Other adverse events are reportable to the MUSC IRB if the AE is unexpected AND related or possibly related AND serious or more prevalent than expected. All three criteria must be met for an AE to be reported to the MUSC IRB. The IRB definition of unexpected is that the AE is not identified in nature, severity or frequency in the current protocol, informed consent, investigator brochure or with other current risk information. The definition of related is that there is a reasonable possibility that the adverse event may have been caused by the drug, device or intervention. Reportable AEs are reviewed by the IRB Chair and reported to the IRB Board at the next meeting.

The potential risks and benefits and methods to minimize these risks are outlined above. The research staff will report any unexpected AEs or any scores of "severe" on the side-effect symptom rating form or any FDA-defined serious AEs to the PI within 24 hours so that the PI can decide on the appropriate action. All unexpected AEs will be monitored while they are active to determine if treatment is needed. Study procedures will follow the FDA's Good Clinical Practice Guidelines (www.fda.gov/oc/gcp).

Data and Safety Monitoring Plan (DSMP). The PI, [name] will be in charge of 1) providing scientific oversight; 2) reviewing all adverse effects or complications related to the study; 3)

monitoring enrollment; 4) reviewing summary reports relating to compliance with protocol requirements; and 5) providing advice on resource allocation. [name] will meet quarterly in person and as necessary with the Col-s as an internal Data Safety Monitoring Committee (DSMC) to review progress. The recommendations of the DSMC will be reviewed and the PI will take appropriate corrective actions as needed. At each meeting the DSMC will:

- Review the research protocol and plans for data and safety monitoring.
- Evaluate the progress of the three studies, including periodic assessments of data quality and timeliness, participant recruitment, enrollment, and retention, participant risk versus benefit, integrity of the intervention, and other factors that can affect study outcome.
- Consider factors external to the study when interpreting the data, such as scientific developments that may impact the safety of study participants or the ethics of the study.
- Make recommendations to the MUSC IRB for continuation or termination of the studies.
- Protect the confidentiality of study data and monitoring.

Institutional Review Board (IRB). The MUSC IRB will review and approve the funded protocol; review patient and provider consent forms, ensure protection of patient privacy and safety, and monitor the study on an ongoing basis. Adverse events will be reported to MUSC IRB as they occur. Annual reports to MUSC IRB will indicate enrollment rates, adverse events, new findings that may influence continuation of the study, and reports of the DSMB.

12.0 Withdrawal of Subjects

Early withdrawal of study subjects. As stated on the Informed Consents, all subjects reserve the right to withdraw from the clinical investigation at any time. The Investigator for any of the following reasons may discontinue subjects from the study:

- Subject is found to have entered the study in violation of the protocol.
- Subject withdraws consent to participate in the study.
- Subject is noncompliant with procedures set forth in the protocol.
- Subject experiences an Adverse Event that warrants withdrawal from the study.
- It is in the Investigator's opinion that it is not in the subject's best interest to continue.
- Subject displays other abnormal laboratory, medical or clinical findings for which clinical intervention should take precedence over study participation including:
 - a) Development of significant neuropsychiatric symptoms
 - b) Generalized seizure
 - c) Inpatient hospitalization
 - d) Unable to complete treatment in the designated time frame

Any participant who informs research staff of an intention to withdraw from the study will be asked to return for a final safety visit, whereby the complete range of post-treatment assessments will be performed. If a participant is lost to follow up, three documented attempts will be made to contact the participant.

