Figure 3. In order to optimize rTMS for neurcognitive enhancement, it is essential to determine the dose-response curve.

accelerated rTMS will promote stress resilience and prevent the onset of neuropsychiatric symptoms (e.g., anxiety, depression, anger, irritability).

Study Arm 1 would establish the dose-response for enhancing cognitive performance with accelerated rTMS to left dIPFC. Stress resilience will be utilized as a secondary outcome. Given the model it would also be reasonable to first establish the objective point at which resilience is up regulated by rTMS. We anticipate that healthy participants analogous to astronauts would likely show little variability in baseline resilience and affective dysfunction. We also anticipate that rTMS as proposed here could prevent the onset of stress and neuropsychiatric symptoms and thus we will longitudinally follow participants for the emergence.

Study Arm 2 would utilize the dose established in study one that maximizes cognitive performance gains while minimizing side effects and burden in a double blind, randomized controlled trial. Primary (neurocognitive performance) and secondary (resilience) outcomes would be identical to study 1. In addition, the impact of active versus sham iTBS on cognitive control and resilience under stress will be demonstrated during a challenging learning paradigm under threat of shock. EEG will be used to assess the impact on of iTBS on neurocircuit structure and function. Response stability will be assessed at 6 months and one year. To assess safety, structural MRI adverse event reporting, and cognitive measures will be collected over a long-term 6-month follow up period.

Study Arm 3 study would assess the biological efficacy of TMS in a microgravity environment during parabolic flight.

Study Arm 4 would establish the dose-response for enhancing cognitive performance with accelerated rTMS to left dIPFC, as well as assessing safety. In addition, the impact of each dose of iTBS on cognitive control and resilience under stress will be demonstrated during a challenging learning paradigm under threat of shock. MRI and EEG will be used to assess the impact on of iTBS on neurocircuit structure and function. Response stability will be assessed at 1 month post-treatment. Approval to combine studies 1 and 2 into a 4th arm was approved by our sponsor, due to recruitment delays caused by COVID-19.

B. INNOVATION AND ADVANTAGES AND RELEVANCE TO ASTRONAUTS

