3.0 Study Endpoints

Study Arms 1 2 & 4 neurocognitive performance is the primary treatment outcome measure. Stress resilience and acceptability/tolerability are secondary treatment outcome measures. For Study Arm 3, biological efficacy of TMS in microgravity is the primary treatment outcome measure. Recruitment for Study Arm 1 will cease once 40 participants have completed all procedures and fulfilled randomization to all doses. Recruitment for Study Arm 2 will cease once 60 participants have completed all procedures and fulfilled randomization to all doses. Recruitment for Study Arm 3 will cease once 10 participants have completed all procedures. Recruitment for Study Arm 4 will cease once 50 participants have completed all procedures and fulfilled randomization to all doses.

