Consent and HIPAA forms will be kept on file for 6 years. Contact information is kept on file for 6 years if the participant consents to allowing their information to remain active in our files, or the contact information is destroyed immediately after the study is completed if participants chose that option on the consent form. Although individual-subject analyses may be written up in publications, the individual subjects producing that data will never be identified by name or initials, or any other identifying information.

All study personnel will complete all annual MUSC CITI training concerning confidentiality and research ethics.

The PI will monitor data quality on a weekly basis to ensure integrity, completeness, and fidelity to the IRB protocol.

Statistical Plan.

Arms 1 and 4. Dose-response relationships for the primary and secondary efficacy endpoints of change in neurocognitive performance (composite measure), EEG, and resilience, stress and symptoms would be assessed using the multiple comparisons procedure with modeling (MCP-Mod) approach for 1 and 2 month outcomes. To determine the reliability of a dose response, MCP-Mod fits a set of pre-specified candidate dose-response curves to the data using a multiple-comparisons technique. The pre-specified dose-response curves to be tested for resilience and neurocognitive performance would be Emax, logistic, and linear. Significant curves would then be used to develop inferences on optimal doses for the randomized controlled trial in aim 2. Descriptive statistics would be performed on acceptability ratings, adverse events, and dropout rates. Linear mixed- effects models would assess the trajectory of pain/discomfort ratings.

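### In Arms 1 and 4 a participant may be discontinued for symptoms that the plan also analyses as an outcome, with no planned 1-month score and recruitment that counts only completers

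*Combined protocol and SAP*

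**What the plan says.** **The ground for leaving.** Section 12.0 states: "The Investigator for any of the following reasons may discontinue subjects from the study". Among the findings where clinical care takes priority over participation it lists "a) Development of significant neuropsychiatric symptoms". The verb is permissive, the removal is from the study rather than only from stimulation, and no scale or threshold is given.

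**The outcome.** For Arms 1 and 4 the Statistical Plan (Section 10.0) names "primary and secondary efficacy endpoints of change in neurocognitive performance (composite measure), EEG, and resilience, stress and symptoms" and analyses them by MCP-Mod at months 1 and 2. The last scheduled assessment in both arms is at 1 month (Section 9.0), so month 1 is used below. Section 2.0 (A6) says stimulation could "prevent the onset of stress and neuropsychiatric symptoms and thus we will longitudinally follow participants for the emergence". Section 3.0 has a shorter list: "Stress resilience and acceptability/tolerability are secondary treatment outcome measures". Symptoms are not named there.

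**Recruitment.** Section 3.0 states: "Recruitment for Study Arm 4 will cease once 50 participants have completed all procedures and fulfilled randomization to all doses". Arm 1 has the same rule with 40. Section 5.0 plans 60 enrolled for 50 completers in Arm 4 and 50 for 40 in Arm 1.

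**Scores for those who leave.** Section 12.0 adds: "Any participant who informs research staff of an intention to withdraw from the study will be asked to return for a final safety visit", with the full post-treatment battery. Neither the Statistical Plan nor Section 12.0 states an analysis set, an estimand or a missing-data method.

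**The concern.** Symptom emergence is something the study sets out to observe. It is also an event that can end observation. Followed as written, the rules can take the participants with the largest symptom increases out of the 1-month analysis and fill their places with people who reached the end.

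The loss runs in one direction. If higher doses provoke symptoms, removals concentrate at those doses and the retained means there look better than the truth. Resilience is affected to the extent that it moves with symptoms. With 50 completers over ten doses there are about five per dose, so one removal can move a dose mean noticeably. A flat or favourable symptom curve could then not be told apart from selective removal.

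**Working it through.** **1. The plan's own figure.** Enrolment = completers / (1 − dropout). For Arm 4, 50/0.90 = 55.6, so 56, and 50/0.80 = 62.5, so 63. The planned 60 lies within the stated 80-90% retention and implies 50/60 = 83.3%. For Arm 1, 40/0.80 = 50, as planned. These figures are not in dispute. They show that up to 60 − 50 = 10 non-completers in Arm 4 can be made up by further recruitment.

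**2. The provisions side by side.**
- Change in symptoms is analysed at a follow-up month (Statistical Plan).
- Significant symptoms may end participation in the study (Section 12.0).
- The final visit is worded for a participant who announces withdrawal. It does not clearly cover removal by the investigator and is not a 1-month measurement.
- Recruitment counts completers (Sections 3.0 and 5.0). Replacement is never stated but follows from this rule.

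**3. Size under a threshold model (inputs assumed).** Let x = (dose step − 1)/9. Symptom change is y = b·x + e, with e standard normal and higher meaning worse. Anyone with y > c is removed and replaced at the same dose. The retained mean at x is b·x − φ(c − b·x)/Φ(c − b·x). Extra enrolment is the sum over doses of 5/(1 − q), minus 50, where q is the share removed at that dose.

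Middle case, b = 0.8 and c = 2: the lowest-dose mean is 0 − 0.055 = −0.055 and the highest-dose mean is 0.8 − 0.219 = 0.581. The least-squares slope over ten doses is 0.64.

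| b (SD) | c (SD) | Removed overall | Observed slope | Attenuation | Extra enrolled |
|---|---|---|---|---|---|
| 0.5 | 2.5 | 1.3% | 0.46 | 7% | 0.7 |
| 0.8 | 2.0 | 6.1% | 0.64 | 20% | 3.3 |
| 1.0 | 1.5 | 17.1% | 0.63 | 37% | 10.8 |

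The last row slightly exceeds the margin of 10, so it is an upper end for this model.

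**4. Size under a case model (inputs assumed).** A case has a shift of s SD, and the risk p rises linearly with dose. A fraction f of cases is removed and replaced at the same dose. The retained mean is s·p(1 − f)/(1 − f·p).

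| Risk, lowest to highest dose | s | Slope, f = 0 | f = 0.25 | f = 0.5 | Loss at f = 0.5 |
|---|---|---|---|---|---|
| 0 to 10% | 2 | 0.20 | 0.15 | 0.11 | 47% |
| 0 to 20% | 3 | 0.60 | 0.47 | 0.33 | 44% |
| 2 to 30% | 3 | 0.84 | 0.68 | 0.50 | 41% |

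For the first row at the highest dose, f = 0 gives 2 × 0.10 = 0.20 and f = 0.5 gives 2 × 0.05/0.95 = 0.105. At f = 1 the slope is zero in every row, because the model gives non-cases no dose effect. In simulation of these scenarios, power to detect the harm at the 5% level is about 7-24% with everyone kept and about 5-13% with half the cases removed.

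**The case against.** The strongest reply is that a permitted event is being treated as a certain one. This stands in part.

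- **Discretion.** A reader might infer that everyone with significant symptoms is removed. Section 12.0 does not say so. The missing threshold does, however, make the selection harder to reproduce.
- **Data may exist.** A reader might infer that removed participants have no outcome data at all. Section 9.0 repeats the symptom and resilience measures after the last session and tracks symptoms weekly, and someone who announces withdrawal is offered a full battery. Symptoms that arise after the 1-month visit lose nothing. But no rule says how earlier scores enter a month-1 analysis.
- **Harm is still recorded.** A reader might infer that Aim 2's criterion of no affective decrement is satisfied automatically. It is not. Adverse events are a separate criterion in Aim 2, an unwanted psychological change counts as one (Section 11.0), and adverse events and dropout are summarised descriptively. Aim 2 was also written for Arm 2, whose mixed models can use partial follow-up.
- **Total loss of signal.** A reader might infer that the slope vanishes. That needs every case removed and no dose effect in the rest. The documents support neither assumption.
- **Low power anyway.** At most about 24% power with full data, in the scenarios tried, limits what any fix can recover. It also argues against discarding the few informative cases.
- **The outcome label.** Section 3.0 does not list symptoms as a secondary outcome, whereas the Statistical Plan includes them among its efficacy endpoints.

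**Conclusion.** The point holds in a limited form. In Arms 1 and 4 the stated rules permit outcome-dependent missingness at month 1, and completer-based recruitment in effect replaces those removed. The bias is towards no harm in every scenario tried. The attenuation is 7-37% in the threshold model and 41-47% if half of all cases are removed. These figures rest on assumed symptom rates, shifts and cut-offs, unit-variance normal scores and same-dose replacement. The documents supply no symptom rate, so the real effect could be negligible if few participants develop symptoms or few are removed. The change is worth making because stated rules produce the problem and the remedy is cheap.

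**What to change.** 1. Leave the clinical ground in Section 12.0 as it is. Add that discontinuation on this ground does not by itself end outcome assessment. Unless consent is withdrawn, the symptom and resilience measures already scheduled (post-treatment, weekly remote, month 1) are still sought.
2. In the Statistical Plan, analyse all treated participants in their randomised dose with all available scores, not only completers. Recruiting another participant does not drop the removed one from the analysis.
3. Report by dose the number discontinued on this ground, counted as cases of emergence.
4. Pre-specify one sensitivity analysis that assigns an unfavourable change score where month 1 is missing for this reason, with the value fixed in advance. A numeric change score fits MCP-Mod. A worst rank does not fit directly, and carrying forward the last score may use a value that predates the symptoms.
5. Reconcile the outcome lists in Section 3.0 and the Statistical Plan.

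The cost is added wording in Section 12.0 and the Statistical Plan and a few extra contacts, for which telephone and REDCap routes already exist. The symptom result may look less favourable.

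### The final safety visit is asked only of participants who choose to leave, not of those the investigator removes for harm

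*Combined protocol and SAP*

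**What the plan says.** Section 12.0 (Withdrawal of Subjects) describes three ways out of the study.

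- **Removal by the investigator.** "The Investigator for any of the following reasons may discontinue subjects from the study". The list includes an adverse event that warrants withdrawal. It also includes findings of the kind the section describes as "clinical findings for which clinical intervention should take precedence over study participation", among them significant neuropsychiatric symptoms, a generalized seizure and an inpatient stay.
- **Withdrawal announced by the participant.** "Any participant who informs research staff of an intention to withdraw from the study will be asked to return for a final safety visit". The content of this visit is broad; the section describes it as one "whereby the complete range of post-treatment assessments will be performed".
- **Loss to follow-up.** Three recorded tries at contact.

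Section 11.0 sets the general end of event follow-up: "the research staff will follow the AE/SAE until resolution, stabilization or until the participant is no longer in the study". Two provisions in the same section go further. For unexpected events, "All unexpected AEs will be monitored while they are active to determine if treatment is needed". For a serious event whose first report is incomplete, "follow-up information will be gathered to enable a complete assessment and outcome of the event".

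Section 1.0 (Aim 2) judges safety on three indices: structural brain change, neurocognitive or affective decrement, and adverse events. Section 5.0 names Arm 4 as the dose-finding and safety arm.

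**The concern.** The exit visit is tied to who makes the decision, not to whether a safety assessment is needed. Several of the investigator's reasons for removal are themselves safety events. For a participant removed for one of them, the event is recorded, but the post-treatment cognitive, affective and MRI measures are not required. The first two Aim 2 indices would then come selectively from people who were not removed. Section 3.0 adds to this: Arm 4 recruits until 50 participants have completed everything, so those who leave are made up with completers.

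The second issue is smaller. If an event is still open when the participant is removed, the general rule in section 11.0 allows follow-up to stop there.

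**Working it through.** The plan gives no figure to reproduce. The check is a reading of the text, followed by a count of what is lost per participant.

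**1. Which exits carry a visit (section 12.0)**

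| Exit route | What the plan requires |
|---|---|
| Participant announces withdrawal | Final safety visit with all post-treatment assessments |
| Lost to follow-up | Three contact attempts |
| Removed by the investigator | Nothing stated |

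The investigator's list also contains withdrawal of consent. A participant in that position who tells staff is covered by the first row, so the gap concerns the other reasons. The ordinary schedule in section 9.0 does not fill it. That schedule describes people in the study, and the separate sentence for those who withdraw would be unnecessary if it applied after exit.

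**2. Which events lose follow-up at exit (section 11.0)**

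- Unexpected event: monitored while active, so not clearly lost.
- Serious event with an incomplete first report: outcome information is gathered, so not clearly lost.
- Expected, non-serious event that is neither resolved nor stable: only the general rule applies, and it can end at study exit. A first-degree burn, named as a risk in section 13.0, would be an example.

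**3. Loss per Arm 4 participant removed during the treatment week**

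Inputs: the Arm 4 schedule in section 9.0 and Table 3. The short symptom and functioning surveys come from Arm 1, whose assessment methods section 9.0 carries over to Arm 4. Baseline measures are taken as complete.

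| Measure | Planned | Not required now | Not required if the final visit is held |
|---|---|---|---|
| Cognitive battery | pre, post, 1 month = 3 | 2 of 3 | 1 of 3 |
| Questionnaire battery | pre, post, 1 month = 3 | 2 of 3 | 1 of 3 |
| Short surveys | 1 intake + 1 post + 4 weekly = 6 | 5 of 6 | 4 of 6 |
| Structural MRI | pre, post = 2 | 1 of 2 | 0 of 2 |

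**4. How many participants this could touch**

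Section 5.0 plans 60 enrolled with 80-90% retention. Early exits from all causes are therefore 60 × (1 − 0.90) = 6 to 60 × (1 − 0.80) = 12. Removals for harm are an unknown part of these. If the ten doses are filled about equally (assumption), 60 / 10 = 6 are enrolled per dose, so a single removal is 1 of about 6 at that dose.

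**5. Time for the visit (Table 3)**

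Cognitive 90 + questionnaires 60 + MRI screen 5 + MRI 60 to 120 = 215 to 275 minutes, or 3.6 to 4.6 hours. The EEG session would add 60 to 120 minutes.

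**The case against.** The other side has several fair points.

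- **The text forbids nothing.** Section 12.0 does not require a visit after removal, but does not rule one out, and staff might well arrange it. The wording may simply be loose, since the investigator's list mixes both kinds of exit. The section also refers to the consent forms, which are not part of the reviewed text. This stands as context, but sections 11.0 and 12.0 still set the rule that staff will follow.
- **Removal from the study is not automatic.** It is discretionary, and section 11.0 separately has staff consider "the need for change or discontinuation in the study intervention". A participant taken off stimulation but kept in the study loses nothing. This stands, and limits the point to people actually removed.
- **The harm is still recorded.** The adverse event definition in section 11.0 is broad enough to take in an observed cognitive or emotional change, and section 13.0 has side effects checked through each day. This stands for the adverse event index. It does not replace standardized scores or the second MRI, on which the other two indices rest.
- **The event follow-up gap is narrow.** An expected event of unexpected severity counts as unexpected and is monitored while active, and a burn is unlikely to lead to removal. This stands. It is the lesser half of the point.
- **The numbers do not measure the problem.** The 6 to 12 exits are all-cause, the removals for harm are probably few, and a visit recovers only one of each measure. After a seizure or hospital stay it may yield less. This also stands, and it is why the point is rated a cheap improvement and no more.

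**Conclusion.** The concern holds. As written, the plan asks people who leave by choice for the measures behind two of the three Aim 2 safety indices, and does not ask people removed for harm. The loss per removed Arm 4 participant is clear; the number of such participants is unknown and probably small. The counts rest on removal falling within the treatment week, on Arm 1's weekly surveys applying in Arm 4, and, for the per-dose figure, on roughly equal allocation. The gap in section 11.0 is clear only for expected, non-serious events still open at removal. Confidence is high, because the conclusion rests on the wording of two sections and on no disputed calculation. This is an inexpensive improvement, not a flaw that undermines the trial.

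**What to change.** Make two one-sentence changes by IRB amendment.

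- **Section 12.0:** *Every participant who stops early, by their own decision or the investigator's, is invited to the final safety visit, with components as clinically appropriate, unless consent is withdrawn.* For example, the threat-of-shock task would be left out after a seizure or psychiatric event, and the Arm 4 post-treatment MRI included where suitable.
- **Section 11.0:** replace the study-exit end point, so that each event is followed *to resolution or stabilization, regardless of study status, unless the participant withdraws consent for follow-up.*

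The weekly surveys and the 1-month visit can stay optional after removal, and the reasons for stopping should remain with the investigators.

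The cost per removed Arm 4 participant who returns is the 3.6 to 4.6 hours shown above, 1 to 2 hours more if the EEG task is kept, and the visit payment. The real downside is added burden on someone who has just had an adverse event, which is why the content is left to clinical judgement.
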